# 6.7.1.1. Adverse Events of Special Interest

Adverse events of special interest (AESI) includes the following events:

- CRS: PT coded as "cytokine release syndrome" and collected on the AE CRF page;
- ICANS: PT coded as "immune effector cell-associated neurotoxicity syndrome" and collected on the AE CRF page;
- Peripheral neuropathy: Standardized MedDRA Queries (SMQ) Peripheral Neuropathy (narrow and broad excluding PTs included in the Guillain-Barre syndrome SMQ) and Guillain-Barre syndrome SMQ (narrow).

CRS and ICANS will be assessed according to ASTCT criteria. All the analyses will be performed for each individual AESI separately.

For CRS and ICANS, the 4 participants who received 44 mg priming dose will be summarized separately within each summary table.

A high-level summary of each AESI will include the number and percent of participants with, separately:

- Any AESI;
- Serious AESI;

- AESI by maximum toxicity grade;
- Had >1 AESI (for CRS and ICANS only);
  - Note: If there are >1 AESI with different grades between two doses, it will be considered as one event;
- Had ICANS concurrent with CRS (for ICANS only). Note: if both CRS and ICANS occurred between the same two doses they will be considered as concurrent;
- AESI leading to dose interruptions;
- AESI leading to dose reductions;
- AESI leading to dose interruptions or reductions;
- AESI leading to permanent discontinuation of study intervention;
- AESI with outcome as resolved.

In addition, the following summary will be provided with descriptive statistics as well as broken down in categories by the time to onset, resolution, and duration of the AESI:

- Time to onset of the AESI;
- Time to resolution of the AESI;
- Duration of each AESI event.

For CRS and ICANS, time relative to dose (ie, after the first dose, after the second dose, after the third dose, after >3 doses) will also be summarized with descriptive statistics.

A summary of AESI symptoms will be provided as follows. The most severe symptom will be summarized if participants have multiple occurrences of AESI symptoms.

- The CRS symptoms (fever, hypoxia and hypotension) as collected on the 'CRS AE' CRFs will be summarized by symptom grade using frequency counts and percentages;
- The ICANS symptoms as collected on the 'ICANS' CRFs will be summarized using frequency counts and percentages;
- The immune effector cell-associated encephalopathy (ICE) scores as collected on the 'ICE' CRFs will be summarized for those participants with ICANS events based on the total ICE scores as follows:
  - ICE score 10;

- ICE score 7-9;
- ICE score 3-6;
- ICE score 1-2;
- ICE score 0.

In addition, the number and percent of participants with CRS/ICANS who received concomitant medications including tocilizumab/steroids (from Concomitant medications CRF) will be summarized.

For peripheral neuropathy, the following summary will be provided:

- Peripheral neuropathy TEAEs by PT and maximum severity grade (all causality and treatment-related);
- Peripheral neuropathy TEAEs and medical history.

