8.3.11. Peripheral neuropathy

Peripheral neuropathy is a common complication of MM and its treatment. Peripheral neuropathy can be caused by MM itself, either by the paraneoplastic effects of the monoclonal protein (polyneuropathy is an essential feature of POEMS syndrome) or in the form of radiculopathy from direct compression, and particularly by certain therapies, including IMiDs and proteasome inhibitors. Symptoms are usually symmetric and include paresthesias, numbness, burning sensation and muscle weakness; these are generally mild, but in rare cases can be disabling or even life-threatening. Treatment-emergent peripheral neuropathy symptoms are usually symmetric, distal and progressive (Richardson et al, 2012). Recently, peripheral neuropathy has been described following administration of BCMA-directed bispecific T-cell engagers (Topp et al, 2020b).

Peripheral neuropathy (including GBS) is considered an important potential risk of elranatamab.

Work-up for new or worsening Grade ≥ 2 peripheral neuropathy should include a neurology consult, imaging (eg MRI of the spine), NCV/EMGs, and lumbar puncture to assess CSF. In consultation with a neurologist, appropriate therapy for peripheral neuropathy (eg, steroids and/or IV immunoglobulin) should be considered.

Closely monitor participants for signs and symptoms of neuropathy following infections or following the administration of any vaccine.

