#### 6.7.1. Adverse Events

All analyses will be based on treatment emergent adverse events (TEAEs) unless otherwise specified. Treatment emergent is defined in Section 3.5. AEs not considered treatment emergent will be flagged in data listings. Summaries of TEAEs due to COVID-19 may be produced if appropriate.

A high-level summary of adverse events (all causality and treatment-related, separately) will include the number and percent of participants with:

- Any TEAEs;
- Serious TEAEs;
- Grade 3-4 TEAEs;
- Grade 5 TEAEs;
- TEAEs leading to dose interruptions;
- TEAEs leading to dose reductions;
- TEAEs leading to dose interruptions or reductions;
- TEAEs leading to permanent discontinuation of study intervention;
- CRS;

- ICANS;
- Peripheral neuropathy.

Seriousness, toxicity grade, and withdrawal from drug are as reported by the investigator on the adverse event CRF.

An event will be considered treatment-related if the investigator considered the event as related to the study drug or if relationship is missing.

For all the AE summaries by SOC and PT, or PT only, the following cytopenias will be clustered. Each participant will be counted only once within each SOC and clustered terms. However, the number of total events will be based on the individual PTs.

- Thrombocytopenia (PT=Thrombocytopenia; Platelet count decreased);
- Anaemia (PT=Anaemia; Haemoglobin decreased, Red blood cell count decreased, Haematocrit decreased, Normochromic anaemia, Normocytic anaemia, Normochromic normocytic anaemia);
- Neutropenia (PT=Neutropenia; Neutrophil count decreased, Neutrophil percentage decreased, Cyclic neutropenia, Agranulocytosis, Granulocytopenia, Granulocyte count decreased);
- Leukopenia (PT=Leukopenia; White blood cell count decreased);
- Lymphopenia (PT=Lymphopenia; Lymphocyte count decreased, Lymphocyte percentage decreased, CD4 lymphocytes decreased, CD4 lymphocyte percentage decreased, CD8 lymphocytes decreased, CD8 lymphocyte percentage decreased).

Summaries by SOC and PT by alphabetical order for SOC and by descending order of frequency for PT in two cohorts combined will be provided for:

- TEAEs (all causality and treatment-related);
- TEAEs by maximum severity grade (all causality and treatment-related);
- TEAEs with Grade 3-4 (all causality and treatment-related);
- TEAEs leading to death (all causality and treatment-related);
- TEAEs leading to dose interruptions (all causality);
- TEAEs leading to dose reductions (all causality);

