Minimum number of participants with Grade 3-4 ICANS events that would lead to a temporary enrollment hold*	4	5	6	7	8	9	10
Minimum number of participants with Grade 4 treatment-related non hematologic events (excluding CRS and ICANS) that would lead to a temporary enrollment hold*	4	5	6	7	8	9	10

Prior distribution: Beta (0.5,0.5)

Criteria for 40 or more evaluable participants will be calculated such that the study will be put on temporary hold if the posterior probability that the true event rate exceeds 20% is  $\geq 0.80$ .

Evaluable participants are defined as those who have received at least 1 dose of study treatment having an identified event or those without such an event who have been followed for at least 28 days from first dose.

\* The study will be put on temporary hold as soon as the minimum number of evaluable participants with the identified AEs has reached the threshold (eg, if there are 4 participants experiencing the identified AE out of the first 6 evaluable participants, the study will be put on hold). A minimum of 4 events are required to trigger a temporary hold.

The criteria for placing the study on temporary hold for the following safety reasons are based on Bayesian posterior probabilities using a non-informative Beta (0.5, 0.5) prior distribution.

- If the number of evaluable participants observed to have treatment-related Grade 3-4 GBS/GB-like AEs results in a posterior probability that the true rate of such events exceeding 3% is ≥0.80, the study will be put on a temporary hold.
- If the number of evaluable participants observed to have treatment-related Grade 4 sensory neuropathy/other IR neurologic AEs (excluding ICANS) or treatment-related Grade 3-4 motor neuropathy results in a posterior probability that the true rate of such events exceeding 10% is ≥0.80, the study will be put on a temporary hold.

Table 7 summarizes the minimum number of evaluable participants with such identified events that would meet the above criteria.

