# Table 7.Minimum Number of Participants with Identified Treatment-Related
Events That Would Prompt Temporary Enrollment Hold (GBS/GB-like
AEs, Peripheral Neuropathy/IR Neurologic AEs)

Number of Evaluable Participants	20-39	40 -64	65-90	91-	117-	145-	
(Cohort A + B)				116	144	150 a	
Minimum number of participants with	2	3	4	5	6	7	
Grade 3-4 treatment-related GBS/GB-like							
events that would lead to a temporary							
enrollment hold*							
Number of Evaluable Participants	20-27	28-35	36-43	44-52	53-60	61-69	70-78 b
(Cohort A + B)							
Minimum number of participants with	4	5	6	7	8	9	10
Grade 4 treatment-related sensory							
neuropathy/IR neurologic AE (excluding							
ICANS) or Grade 3-4 treatment-related							
motor neuropathy events that would lead							
to a temporary enrollment hold**							

Prior distribution: Beta (0.5,0.5)

a. Criteria for 151 or more evaluable participants will be calculated such that the study will be put on temporary hold if the posterior probability that the true event rate exceeds 3% is ≥0.80.

b. Criteria for 79 or more evaluable participants will be calculated such that the study will be put on temporary hold if the posterior probability that the true event rate exceeds 10% is ≥0.80.

Evaluable participants are defined as those who have received at least 1 dose of study treatment having an identified event or those without such an event who have been followed for at least 28 days from first dose.

- \* The study will be put on temporary hold as soon as the minimum number of evaluable participants with the identified AEs has reached the threshold (eg, for GBS/GB-like AEs, if there are 2 participants experiencing the identified AE out of the first 10 evaluable participants, the study will be put on hold). A minimum of 2 events are required to trigger a temporary hold.
- \*\* The study will be put on temporary hold as soon as the minimum number of evaluable participants with the identified AEs has reached the threshold (eg, if there are 4 participants experiencing the identified AE out of the first 15 evaluable participants, the study will be put on hold). A minimum of 4 events are required to trigger a temporary hold.

The list of search criteria for IR neurologic AE PT is defined in Appendix 3. Further clinical review is required to determine if a specific event meets the criteria.

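### Read literally, the peripheral neuropathy AESI search drops any neuropathy term that lies in the broad scope of the Guillain-Barré SMQ

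*SAP*

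**What the plan says.** SAP 6.7.1.1 lists three adverse events of special interest: CRS, ICANS and peripheral neuropathy. The first two are each identified by a single preferred term (PT). Peripheral neuropathy is identified by "Standardized MedDRA Queries (SMQ) Peripheral Neuropathy" ("narrow and broad excluding PTs included in the Guillain-Barre syndrome SMQ) and Guillain-Barre syndrome SMQ (narrow").

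The same section then states: "All the analyses will be performed for each individual AESI separately". The outputs built on each AESI include any, serious and maximum-grade counts; counts leading to interruption, reduction or discontinuation; and time to onset, time to resolution and duration. For this AESI the section adds "Peripheral neuropathy TEAEs by PT and maximum severity grade (all causality and treatment-related") and a summary against medical history. The high-level AE summary in SAP 6.7.1 also has a peripheral neuropathy line, and the SAP gives no other definition for it.

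Protocol 8.3.11 sets the importance of the topic: "Peripheral neuropathy (including GBS) is considered an important potential risk of elranatamab".

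**The concern.** The exclusion and the add-back do not match. The exclusion names the Guillain-Barré SMQ without limiting its scope; the add-back is limited to narrow. A term removed by the first clause is restored by the second only if it is Guillain-Barré narrow. A term that belongs to the Peripheral Neuropathy SMQ and is Guillain-Barré broad is removed and not restored.

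At stake is the completeness of the pooled safety summary for a designated important risk. The protocol amendment history shows that this risk led to regulator-requested changes to eligibility, dose modification and hold rules (Amendments 5 and 6). The AESI outputs are the planned adverse-event tables that pool neuropathy terms, count each participant once, and give onset, resolution and duration. Tables by individual PT do not do that.

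**Working it through.** The plan states no figure here to reproduce, so the check is of the set logic.

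**Notation.** P is the Peripheral Neuropathy SMQ, narrow and broad together. G is the whole Guillain-Barré SMQ. Gn is its narrow terms. Gb is G minus Gn, the terms that are in that query only through its broad scope.

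**Literal search:** (P minus G) plus Gn.

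**Plain union for comparison:** P plus Gn.

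**Difference:** union minus literal search = terms in P and in G but not in Gn = P ∩ Gb.

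Terms in both P and Gn are removed and then restored, so for them the exclusion does nothing. Its only possible net effect is to drop P ∩ Gb.

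**All nine combinations of scope, under three readings of the exclusion:**

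| Neuropathy SMQ | Guillain-Barré SMQ | Literal | Exclusion applies to neuropathy-broad terms only | Exclusion limited to Guillain-Barré narrow | Plain union |
|---|---|---|---|---|---|
| none | none | out | out | out | out |
| none | narrow | in | in | in | in |
| none | broad | out | out | out | out |
| narrow | none | in | in | in | in |
| narrow | narrow | in | in | in | in |
| narrow | broad | **out** | in | in | in |
| broad | none | in | in | in | in |
| broad | narrow | in | in | in | in |
| broad | broad | **out** | **out** | in | in |

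The literal reading loses two cells against the union, the second reading loses one, and the third loses none. A term that is Guillain-Barré broad but outside the Peripheral Neuropathy SMQ is in none of the searches, so it is not part of this point.

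**What a lost term does to the outputs.** A participant whose only qualifying terms lie in P ∩ Gb leaves the AESI count. A participant who also has another qualifying term stays in, but the maximum grade can only fall and the first onset can only move later.

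**Size.** Let f be the share of participants in the union-based AESI whose only qualifying terms lie in the overlap. Then reported rate = union-based rate × (1 − f). The documents give neither quantity. Purely as arithmetic, assume a union-based rate of 15% among the 187 treated participants (123 + 64, Protocol 9.2), or about 28:

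- f = 0: 15.0%, 28 participants
- f = 0.1: 15% × 0.9 = 13.5%, about 25
- f = 0.3: 15% × 0.7 = 10.5%, about 20

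The 15% and the values of f are assumptions that show how the formula behaves. They are not estimates for this trial.

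**Whether the documents settle f.** They do not. SAP Appendices 2 and 3 list cytopenia and immune-related neurologic terms only. No PT list is given for this AESI, and SAP 3.5.1 ties coding to whichever MedDRA version is current, without a number.

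**The case against.** The strongest reply is that the clause may be deliberate. If a plain union had been meant, no exclusion would be needed, and its only net effect is to keep out terms that are Guillain-Barré broad. That would fit a wish to avoid non-specific terms. The reply cannot be ruled out, because the SAP gives no rationale either way. It fits the text poorly, though: the same search keeps neuropathy-broad terms while, read literally, it drops even neuropathy-narrow terms that happen to be Guillain-Barré broad.

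A second reply is that the clause only prevents double counting of the narrow terms named next. On that reading nothing is lost. But it requires a scope limit that the text does not contain, and a definition whose readings give different term lists needs clarifying in any case.

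Two stronger readings are tempting and are not supported:

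- A reader might infer that the affected events are counted nowhere. They are not lost to the report. SAP 6.7.1 says "Summaries by SOC and PT by alphabetical order for SOC and by descending order of frequency for PT in two cohorts combined will be provided", covering all, graded, serious and fatal events and those leading to dose change or discontinuation. Neurological examinations (SAP 6.7.6) and QLQ-CIPN20 scores (SAP 6.4.4) are summarized separately. Nor does the search drive the enrollment hold. SAP 7.1.2 defines that rule by event type and grade ("If the number of evaluable participants observed to have treatment-related Grade 4 sensory neuropathy/other IR neurologic AEs (excluding ICANS")), and for the immune-related neurologic term list it adds "Further clinical review is required to determine if a specific event meets the criteria".
- A reader might infer that the AESI is in fact under-counted. That needs at least one term in P ∩ Gb and a participant whose AESI count depends on it. The wording shows that the authors expected the two queries to share terms. It does not show that any shared term is in the broad part; all of them could be narrow, and then nothing is lost.

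**Conclusion.** The definition is defective as worded. Read literally, its exclusion can only remove neuropathy terms from the AESI, and it does so without a stated reason. Any effect on the number of participants with the AESI is an under-count. Its size is unknown and is zero if no Peripheral Neuropathy term is Guillain-Barré broad, or if the exclusion is applied in practice to narrow terms only.

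The consequence is confined to the peripheral neuropathy AESI outputs and, if it uses the same definition, the peripheral neuropathy line of the high-level AE summary. These are descriptive. The primary endpoint, alpha, power, general AE tables and hold rules are unaffected. The point merits correction because the topic is a designated important risk, the possible error runs in one direction, and the SAP does not show which terms drop out.

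**What to change.** Either of two changes to SAP 6.7.1.1 restores exactly the lost cells and alters no other:

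- limit the exclusion to PTs in the narrow scope of the Guillain-Barré SMQ, which also suits a layout with neuropathy and Guillain-Barré on separate rows; or
- remove the exclusion and define the AESI as any PT in the Peripheral Neuropathy SMQ (narrow and broad) or the Guillain-Barré SMQ (narrow), with each participant counted once.

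State the MedDRA version used for the search and append the resulting PT list, as Appendices 2 and 3 already do for other groupings. If leaving out Guillain-Barré broad terms was intended, say so, give the reason and list the excluded PTs.

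The cost is one phrase and an update to the PT selection list. The small downside is that some less specific terms may enter the AESI, in a search that already accepts broad neuropathy terms.

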# 6.7.1.2. Other Adverse Events of Clinical Interest

Other adverse events of clinical interests (oAECIs) include the following events:

- Infections:
  - The MedDRA SOC of Infections and infestations.
- Cytopenias:
  - The MedDRA PTs for cytopenias are defined in Appendix 2.
- Hypogammaglobulinemia:
  - Including the MedDRA PTs: Blood immunoglobulin G decreased, Hypogammaglobulinaemia, Hypoglobulinaemia, Immunoglobulins decreased and Globulins decreased.
- Injection site reactions:
  - The MedDRA HLT of Injection site reactions.
- Secondary malignancies:
  - The MedDRA SOC of Neoplasms Benign, Malignant and Unspecified.

All the analyses will be performed by each individual oAECI separately. For cytopenias, the individual PTs (ie, not clustered terms) will be reported in the summary.

A high-level summary of each of oAECI will be provided including the following, if applicable:

- Any oAECIs;
- Serious oAECIs;
- oAECIs by maximum toxicity grade;
- oAECIs leading to dose interruptions;
- oAECIs leading to dose reductions;
- oAECIs leading to dose interruptions or reductions;
- oAECIs leading to permanent discontinuation of study intervention.

The following summary will be provided for each oAECI, if applicable:

- oAECI by PT and maximum severity grade (all causality and treatment-related);
- Time to onset of the oAECI, time to resolution, and duration of the oAECI with descriptive statistics as well as broken down in categories.

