Hypogammaglobulinemia/ Subcutaneous or Intravenous immunoglobulin (IVIG)	Monitor immunoglobulin levels for the occurrence of hypogammaglobulinemia.	Administration of immunoglobulin for IgG level ≤400 mg/dL is strongly recommended	Until resolution of hypogammaglobulinemia
Neutropenia/G-CSF Prophylaxis	Prophylactic or therapeutic administration of G-CSF in participants with severe neutropenia or with serious neutropenic complications should be considered by investigators consistent with the ASCO guidelines (Smith et al, 2015) in order to decrease the risk of neutropenia specifically in participants with baseline extensive BM involvement and/or low neutrophil counts.	For participants with ANC <1000/µL	Until resolution of neutropenia.

Dimopoulos et al, 2021; NCCN 2022b NCCN 2022c; NCCN 2022a; Smith et al, 2015; Raje et al, 2022.

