# Appendix 2. List of MedDRA Preferred Terms for Cytopenia

- Cytopenia;
- Bicytopenia;
- Pancytopenia;
- Full blood count decreased;
- Bone marrow failure;
- Myelosuppression;
- Red blood cell count decreased;
- Haematocrit decreased;
- Haemoglobin decreased;
- Anaemia;
- Normochromic anaemia;
- Normocytic anaemia;
- Normochromic normocytic anaemia;
- Leukopenia;
- Agranulocytosis;
- Granulocytopenia;
- Granulocyte count decreased;
- White blood cell count decreased;
- Neutropenia;
- Neutrophil count decreased;
- Neutrophil percentage decreased;
- Band neutrophil count decreased;
- Band neutrophil percentage decreased;
- Cyclic neutropenia;

- Metamyelocyte count decreased;
- Lymphopenia;
- Lymphocyte count decreased;
- Lymphocyte percentage decreased;
- CD4 lymphocytes decreased;
- CD4 lymphocyte percentage decreased;
- Thrombocytopenia;
- Platelet count decreased;
- Platelet production decreased.

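### The closed term list for the cytopenia oAECI omits two CD8 terms that the SAP itself counts as lymphopenia, and does not include febrile neutropenia

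*SAP*

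**What the plan says.** SAP 6.7.1.2 names five groups of oAECI. Infections and secondary malignancies are each defined by a whole system organ class (SOC), and injection site reactions by a high level term. Hypogammaglobulinemia is given by a PT list with open wording: "Including the MedDRA PTs: Blood immunoglobulin G decreased, Hypogammaglobulinaemia, Hypoglobulinaemia, Immunoglobulins decreased and Globulins decreased". Cytopenias are tied to a separate list: "The MedDRA PTs for cytopenias are defined in Appendix 2". The same section adds: "For cytopenias, the individual PTs (ie, not clustered terms) will be reported in the summary".

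For each oAECI the section plans, where applicable, counts of participants with any event, serious events, events by maximum grade, and events leading to interruption, reduction or permanent discontinuation. It also plans a table by PT and maximum grade, and summaries of time to onset, time to resolution and duration.

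SAP 6.7.1 separately defines five cytopenia clusters for the general adverse-event tables. Its lymphopenia cluster ends with "CD8 lymphocytes decreased, CD8 lymphocyte percentage decreased". In SAP Appendix 2 the lymphocyte entries end with "CD4 lymphocyte percentage decreased", and the next entry is thrombocytopenia. The neutropenia cluster in 6.7.1 reads "Neutropenia (PT=Neutropenia; Neutrophil count decreased, Neutrophil percentage decreased, Cyclic neutropenia, Agranulocytosis, Granulocytopenia, Granulocyte count decreased". Febrile neutropenia is in neither that cluster nor Appendix 2.

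**The concern.** A safety table built from a closed term list is only as complete as the list. Nothing in 6.7.1.2 lets a programmer add an unlisted PT. Because the table reports individual PTs, the 6.7.1 clusters do not bring a missing term back in.

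There are two gaps. The first is internal: the SAP treats the two CD8 terms as cytopenia in one place and not in another. The second is a term that a reader would expect in a cytopenia summary for this drug. The risk table in Protocol 2.3.1 says that elranatamab likely contributes to worsening neutropenia, and asks for infection monitoring especially in neutropenic participants. Protocol Appendix 14 anticipates the clinical situation: "administration of G-CSF in participants with severe neutropenia or with serious neutropenic complications should be considered". That sentence is about supportive care and does not govern term selection, but it shows that complicated neutropenia is foreseen.

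What is at stake is the accuracy of the pooled cytopenia rows, which a reader will take as the trial's summary of this harm.

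**Working it through.** No power, alpha or sample-size figure bears on this point, and the plan states no figure to reproduce. The check is a term-by-term comparison of two SAP lists.

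**Inputs.** List 1 is SAP Appendix 2, with 33 distinct PTs. List 2 is the five clusters in SAP 6.7.1, with 2 + 7 + 7 + 2 + 7 = 25 distinct PTs.

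**Step 1: are the cluster PTs in Appendix 2?**

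| Cluster (SAP 6.7.1) | PTs in cluster | Found in Appendix 2 | Missing |
|---|---|---|---|
| Thrombocytopenia | 2 | 2 | none |
| Anaemia | 7 | 7 | none |
| Neutropenia | 7 | 7 | none |
| Leukopenia | 2 | 2 | none |
| Lymphopenia | 7 | 5 | CD8 lymphocytes decreased; CD8 lymphocyte percentage decreased |
| Total | 25 | 23 | 2 |

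**Step 2: the reverse comparison.** 33 − 23 = 10 Appendix 2 PTs are in no cluster: Cytopenia, Bicytopenia, Pancytopenia, Full blood count decreased, Bone marrow failure, Myelosuppression, the two band-neutrophil terms, Metamyelocyte count decreased and Platelet production decreased. Appendix 2 is therefore the broader list everywhere except at CD8. An oversight is a plausible explanation: by the SAP version history, Appendix 2 came in with version 3 and clustering with version 4.

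**Step 3: febrile neutropenia.** No entry in either list contains the word febrile.

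**Step 4: which rows change.** For a participant with an event coded to one of the three PTs:

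- The any-cytopenia row loses the participant only if no listed PT was also reported.
- The serious, interruption, reduction and discontinuation rows lose the participant only if no listed PT for that participant meets the same condition.
- The maximum-grade row is too low if the omitted PT carries the highest grade.
- Onset, resolution and duration leave out the omitted event.

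**Step 5: can the general tables repair this?** Only in part. Febrile neutropenia would have its own PT row there. A CD8 event would be folded into the lymphopenia cluster, because 6.7.1 applies clustering to all SOC/PT summaries. The pooled oAECI rows count participants across PTs, and one participant may have several, so adding PT rows does not recover them. Cytopenia onset, resolution and duration are planned only in 6.7.1.2.

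**Step 6: size per participant.** With the enrolled and treated numbers in Protocol 9.2, one affected participant is 1/123 = 0.8 percentage points in Cohort A, 1/64 = 1.6 in Cohort B and 1/187 = 0.5 overall (123 + 64 = 187). These are units of change, not estimates of the effect.

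**Step 7: after the fix.** Appendix 2 would have 33 + 3 = 36 PTs and would cover all 25 cluster PTs.

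**The case against.** The sponsor may define its own event groupings, and much of the information is reported elsewhere. SAP 6.7.1 tabulates all treatment-emergent events by SOC and PT, including by maximum grade, for serious events, and for those leading to interruption, reduction or discontinuation. SAP 6.7.3 grades neutrophil and lymphocyte counts from laboratory data, with shift tables, however the adverse event was coded. The CD8 gap probably matters little: the safety tests in Protocol Appendix 2 include lymphocytes but no CD8 subset, and the dose-modification table treats lymphopenia as expected from the mechanism. All of this stands and limits the weight of the point. It does not restore the pooled participant-level rows or the timing summaries.

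Three stronger readings are tempting, and the documents do not support them.

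- A reader might infer that the table leaves out the most serious form of cytopenia. Neither document names febrile neutropenia or ranks cytopenias, and Appendix 2 keeps agranulocytosis, pancytopenia and bone marrow failure. The CD8 terms carry no severity argument.
- A reader might infer that the SAP will print two conflicting lymphopenia counts. The oAECI table has no clustered lymphopenia row, so there is no such pair. The conflict is in which PTs count as cytopenia.
- A reader might infer that the cytopenia rates will certainly be too low. That depends on participants with no listed PT meeting the same row, and the documents hold no event data.

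It is also fair to say that cytopenia is not an entry of its own in the protocol risk table. Neutropenia appears there under infections.

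**Conclusion.** The point holds as a minor one. The CD8 mismatch is proven from the SAP alone: two of 25 cluster PTs are absent from the list that defines the cytopenia oAECI. The absence of febrile neutropenia from both lists is also a matter of record.

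That this absence leads to missed events rests on an assumption from outside the documents: that febrile neutropenia is coded as a PT of its own. On the further assumption that it sits outside the infections SOC, the infection oAECI would not pick it up either. If such an event were instead coded to a listed PT, nothing would be lost.

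The consequence is a possible undercount or under-grading in the descriptive cytopenia oAECI rows, and incomplete onset, resolution and duration summaries. The number of participants affected is not known from the documents. No endpoint or clinical management is involved. The temporary-hold rules in SAP 7.1.2 do not use this list.

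**What to change.** In SAP Appendix 2, add CD8 lymphocytes decreased and CD8 lymphocyte percentage decreased, so that every PT in the 6.7.1 clusters is also in the oAECI list. Add febrile neutropenia to Appendix 2 as well, shown as its own PT row within the cytopenia oAECI. The existing rule of reporting individual PTs needs no change.

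The cost is three entries in an appendix and the matching update to the table programs. The one downside is that the reported cytopenia oAECI rates may rise slightly.
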